10.2.8 Subgroup Analysis

Sub-group analyses on performance, effectiveness, and safety endpoints are planned. These analyses are exploratory in nature and may include certain baseline demographics, disease characteristics, echocardiography parameters, and procedural characteristics selected by investigators and sponsor aimed at a comprehensive understanding of device performance and safety profile.

10.2.9 Handling of Missing Data

Primary analyses will consist of all available data evaluated under ITT principles, referred to in International Conference on Harmonization module E9 (Statistical Principles for Clinical Trials)

as the full analysis set. Consequently, data will only be absent from analyses of study outcomes in the event that they were not available for collection.

In general, missing values in any of the endpoints will not be inputted when summarizing these endpoints using descriptive statistics.

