3.1 Primary Safety Endpoint

The primary safety endpoint will evaluate the procedural and device safety of the Tendyne Mitral Valve System. The composite endpoint is: Device Success (defined below) and freedom from device or procedure related serious adverse events (SAEs) at 30 days post implant, as classified by the Clinical Events Committee (CEC).

Definition of Device Success:

All of the following must be present:

- 1) Absence of procedural mortality or stroke; and
- 2) Proper placement and positioning of the device, and
- 3) Freedom from unplanned surgical or interventional procedures related to the device or access procedure; and
- 4) Continued intended safety and performance of the device, including:
 - a) No evidence of structural or functional failure
 - b) No specific device-related technical failure issues or complications
 - c) Reduction of MR to either optimal or acceptable levels without significant structural valve dysfunction and with no greater than mild (1+) paravalvular MR (and without associated hemolysis).

Structural failure is when the valve fails to perform as intended due to a complication related the valve, such as: fracture, migration or embolization. Functional failure is when the valve performs as intended without complication but does not adequately reduce the degree of MR or results in new, significant mitral stenosis.

Post-procedure MR reduction is considered optimal when reduced to trace or absent and acceptable when reduced by at least 1 class or grade from baseline and to no more than moderate (2+) residual MR in severity [25].

Note: Criterion #4c above has been modified from the MVARC guidelines [25], to align with the structural valve dysfunction definition used in this CIP.

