3.2 Clinical Endpoints

The following clinical endpoints will be evaluated:

- Technical success evaluated upon exit from procedure room, defined as:
 - 1) Absence of procedural mortality; and
 - 2) Successful access, delivery and retrieval of the device delivery system; and
 - 3) Successful deployment and correct positioning of the intended device; and
 - 4) Freedom from emergency surgery or re-intervention related to the device or access procedure
- Patient Success evaluated at 1, 2, 3, 4, and 5 years post index procedure, defined as:
 - 1) Device Success (either optimal or acceptable); and
 - 2) Subject returned to the pre-procedural setting (e.g. home, assisted living facility); and
 - 3) No transcatheter or surgical re-interventions for mitral valvular disease (modified from MVARC guidelines); and
 - 4) Improvement from baseline symptoms (NYHA improvement by ≥ 1 Functional Classification); and
 - 5) Improvement from baseline in functional status (6MWD improvement by ≥ 50 meters); and
 - 6) Improvement from baseline in Quality of Life (KCCQ improvement by ≥ 10 points)
- Device Success as measured at 30 days and at all post-procedural intervals
- Freedom from all-cause mortality at 3 months, 6 months, 1 year, and then annually through 5 years post index procedure
- Distance walked on the 6MWT at baseline, 30 days, 3 months, 6 months, 1 year, and then annually through 5 years post index procedure (change from baseline to follow-up)
- KCCQ QoL scores at baseline, 30 days, 3 months, 6 months, 1 year, and then annually through 5 years post index procedure (change from baseline to follow-up)
- NYHA Functional Classification at baseline, 30 days, 3 months, 6 months, 1 year, and then annually through 5 years post index procedure

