10.2 Data Analysis Plan

10.2.1 General Principles

All statistical analyses will be performed using Statistical Analysis System (SAS) for Windows (version 9.4, SAS Institute Inc. Cary, NC) or other widely accepted statistical or graphical software.

Descriptive statistics will be used to present the data and to summarize the results. Discrete variables will be presented using frequency distributions and cross tabulations. Continuous variables will be summarized by presenting the number of observations (N), mean, standard deviation, median, minimum, and maximum values.

In general, data for all study subjects combined will be presented. The primary analysis for all baseline characteristics and study outcomes will include all available data for all enrolled subjects. Individual data will be presented in subject listings.

Summaries of the following endpoints present the number and percentage of unique subjects with an event, unless specified otherwise: protocol deviations; subject status; study medications; adverse events. Thus, multiple occurrences of the same event are counted only once per subject, unless specified otherwise.

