10.2.4 Analysis Samples

The primary analysis sample will be based on the principle of intention-to-treat (ITT). All statistical analyses in this study will be “intent to treat” with enrolled subjects with attempted device implant included in the analysis. As-treated analysis will also be conducted, which includes subjects with study device remain implanted.

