10.2.7 Analysis of Clinical Endpoints

Definition of clinical endpoints are described in **Section 3.2**.

For composite endpoints, i.e., technical success, patient success, and device success, the number and percentage of subjects with success will be summarized. Descriptive statistics for components of each endpoint will also be provided.

For continuous variables (e.g., KCCQ scores and 6MWT distances), results will be summarized with the numbers of observations, means, standard deviations, minimums, maximums, and 95% confidence intervals. Change from baseline will be included using these same descriptive statistics.

For categorical variables such as mortality and NYHA classification, results will be summarized with subject counts and percentages/rates, and with 95% confidence intervals.

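### Patient Success at 1 to 5 years has no rule for subjects who die before the visit, and the available-data rule, taken literally, lets them drop out of the percentage

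*Combined protocol and SAP*

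**What the plan says.** **Endpoint.** Section 3.2 of the protocol has "Patient Success evaluated at 1, 2, 3, 4, and 5 years post index procedure, defined as" six items joined by 'and': Device Success, return to the pre-procedure living setting, no mitral re-intervention, and improvement by set amounts in NYHA class, six-minute walk distance and KCCQ. Survival is not among them. The only explicit death term comes through the Device Success item, whose definition in 3.1 begins "All of the following must be present" and lists "Absence of procedural mortality or stroke". Freedom from all-cause mortality is a separate clinical endpoint in 3.2.

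**Analysis.** For the composites, 10.2.7 says "the number and percentage of subjects with success will be summarized", plus descriptive statistics for the components. It gives no denominator for each visit.

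**Sample.** Section 10.2.4 calls every analysis intention-to-treat, with "enrolled subjects with attempted device implant included in the analysis".

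**Missing data.** Section 10.2.1 says "The primary analysis for all baseline characteristics and study outcomes will include all available data for all enrolled subjects". Section 10.2.9 adds that "data will only be absent from analyses of study outcomes in the event that they were not available for collection", and then: "In general, missing values in any of the endpoints will not be inputted when summarizing these endpoints using descriptive statistics".

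**SAP.** Section 10.1 leaves further detail to a Statistical Analysis Plan. The text available for review contains no rule for scoring deaths.

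**The concern.** A subject who dies before, say, the 2-year visit has no 2-year NYHA class, walk distance or KCCQ score. On the face of 10.2.9 those values could not be collected, so they may be absent, and they are not filled in. An analyst following that text could leave the subject out of both numerator and denominator. Patient Success would then describe survivors who came for testing, not everyone in whom an implant was attempted.

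Some deaths can fail on items already listed: a procedural death, a death from a device complication, or a death after mitral re-intervention. The gap concerns the rest. Follow-up lasts five years, and sections 2.2.2 and 2.3.2 describe serious co-morbidity in this population, so such deaths are foreseeable.

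What is at stake is how a descriptive percentage is read, not a test result. It still matters, because 2.4.1 says the findings may refine the intended population or support later protocols, and section 15 commits to public reporting of the pre-specified outcomes.

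**Working it through.** The plan states no expected Patient Success rate and no expected mortality, so there is no figure of its own to reproduce. The check is in two steps.

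**Step 1: which reading does the text support?**

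- *Non-success.* Section 10.2.4 puts all attempted implants in every analysis. Section 3.2 requires all six items. Section 10.2.7 counts subjects with success, and a subject who died cannot be shown to have the three gains.
- *Dropped.* Sections 10.2.1 and 10.2.9 analyse available data, accept absence where data could not be collected, and in general do not impute. Section 10.2.9 applies this under intention-to-treat principles, so that label alone does not settle the scoring.

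Section 10.2.4 says who belongs to the sample. It does not say how an unmeasured outcome in a sample member is scored. The first reading is the more natural, and the second is permitted.

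**Step 2: how far apart are the two percentages?**

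Inputs:
- N = 30, the planned maximum (sections 4.2 and 10.1), with every subject due at the visit.
- d = deaths before the visit that have not already failed on an observed item. Assumed, 0 to 9.
- s = successes at the visit, the same under both readings. Assumed, set by a success rate p among survivors of about 20% to 70%.
- No other missing data.

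The only mortality rate in the document, 19 of 64 in section 2.2.2, is periprocedural and concerns other valves. It is not used.

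Formulas:
- Deaths scored as non-success: s/30
- Deaths dropped: s/(30 − d)
- Gap: s/(30 − d) − s/30 = s·d / [30(30 − d)] = p·d/30, where p = s/(30 − d)

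The gap is never negative. It is zero when d = 0 or s = 0. Each dropped death adds p/30: 0.7 points at p = 20% and 2.3 points at p = 70%.

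Results (exact Clopper-Pearson 95% intervals in brackets):

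| d | s | Deaths dropped | Deaths as non-success | Gap (points) |
|---|---|---|---|---|
| 0 | any | s/30 | s/30 | 0 |
| 1 | 6 | 6/29 = 20.7% | 6/30 = 20.0% | 0.7 |
| 3 | 16 | 16/27 = 59.3% | 16/30 = 53.3% | 5.9 |
| 6 | 5 | 5/24 = 20.8% (7.1–42.2) | 5/30 = 16.7% (5.6–34.7) | 4.2 |
| 6 | 14 | 14/24 = 58.3% (36.6–77.9) | 14/30 = 46.7% (28.3–65.7) | 11.7 |
| 9 | 15 | 15/21 = 71.4% (47.8–88.7) | 15/30 = 50.0% (31.3–68.7) | 21.4 |

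The last row is the extreme of the assumed grid, not a forecast. It needs nine deaths of this kind together with high success on a demanding composite, and nothing in the document supports that combination. The intervals are wide, and in each of the last three rows the two overlap heavily. The gap is nevertheless a difference of definition on the same data, not sampling error.

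**The case against.** **The default reading already works.** With all items required and an intention-to-treat sample, a dead subject is simply not a success. This is a strong point, and it is why the text permits dropping deaths but does not require it. A reader might infer that the plan instructs analysts to exclude deaths; no sentence does. Listing death as a reason for discontinuation in 5.3 ends follow-up and says nothing about scoring.

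**A reader can correct the figure.** The success count is reported and is the same either way. Section 10.2.2 summarises discontinuations by reason, 10.2.1 promises subject listings, and mortality is reported separately. Anyone can therefore recompute s/30. This stands and lowers the importance of the point. It does not remove the need for the headline percentage to have a fixed denominator, chosen before the deaths are known.

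**The SAP may cover it.** Possibly. The conclusion is limited to the text available.

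**Device Success after 30 days.** A reader might infer the same fault there and want every death scored as failure. The documents do not support that. A late death unrelated to the device or procedure breaches no listed Device Success item, and all-cause mortality is a separate endpoint. Scoring such a death as device failure would redefine the endpoint, and if done only after 30 days would give one name two meanings. It is also arguable there whether the subject is a success on the last assessment, missing or a failure. That is a choice about what the endpoint means, not an error.

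**Conclusion.** The point holds for Patient Success at 1 to 5 years. The plan has an available-data, no-imputation rule that, taken literally, allows a survivors-only percentage, and no statement that overrides it for deaths. Relative to non-success scoring, the effect can only favour the device or be nil: p·d/30, which is 0 with no deaths and 11.7 points in the six-death, 14-success illustration. Those sizes rest on assumed deaths and success rates with 30 subjects due and no other missing data.

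The point is worth fixing, but its consequences are modest. Section 10.1 sets no hypothesis test, section 3 sets no pass or fail criterion, and the success count and mortality are reported in any case. It does not show that the 30-day primary safety endpoint or the Device Success definition is wrong. Confidence is high for the text as supplied; a separate SAP could already contain the rule.

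**What to change.** In 10.2.7 and 10.2.9, and in the SAP, state for Patient Success only:

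1. The denominator at each visit is all attempted implants due at that visit, including subjects who died earlier.
2. Death from any cause before the visit counts as non-success.
3. Any observed failed component fails the composite, even if other components are missing.
4. Living subjects who cannot be classified are reported separately as missing. They are not silently treated as failures.
5. The numbers dead, missing and evaluable are shown at each visit, with the available-case percentage as a sensitivity analysis.

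Leave the Device Success definition unchanged at every visit, including within the 30-day primary composite. Print the number of deaths and the number evaluable beside each Device Success percentage.

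**Cost.** A short amendment, with IRB submission and approval before implementation under section 14, and possibly a lower reported success rate. No new clinical assessment is needed, and 5.3 already obtains vital status for withdrawn subjects. The weak spot is loss to follow-up: under 12.8 a death-index check is something sites may be asked to do, so the rule depends on those checks actually being made.

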11 DIRECT ACCESS TO SOURCE DATA / DOCUMENTS

The investigator/institution will permit and assure direct access to source data/documents (e.g., hospital/clinic/office charts, catheterization reports, laboratory results) in order for clinical investigation-related monitoring, audits, IRB review and regulatory inspections to be performed.

Subjects providing informed consent are agreeing to allow Sponsor and/or its designee access and copying rights to pertinent information in their medical records concerning their participation in this feasibility study.

The investigator will obtain, as part of the informed consent, permission for Sponsor monitors and designees, including auditors, or regulatory authorities to review, in confidence, any records identifying the subjects in this study. This information may be shared with regulatory agencies; however, per relevant confidentiality and privacy rules (HIPAA), the Sponsor and its designees will not otherwise release the subject's personal, private and protected health information.

12 QUALITY CONTROL AND QUALITY ASSURANCE

To ensure the study is conducted in accordance with the CIP and that both the Sponsor and investigational sites are in compliance, proper quality control and assurance procedures will be followed in this study. These controls include the establishment of training, monitoring, support of quality audits and study committees.

12.1 Selection of Clinical Sites and Investigators

The Sponsor will select investigational sites after review of a site assessment and the qualifications of the proposed investigators at the site. Each site will be required to have a Principal Investigator (either an interventional cardiologist or cardiothoracic surgeon) and a multidisciplinary team. The multidisciplinary team will consist of a minimum of the following:

- One (1) Interventional Cardiologist
- One (1) Cardiothoracic Surgeon
- One (1) Echocardiographer

Investigators must be qualified by education, training, and experience to assume responsibility for the proper conduct of human subject research. Investigators must use best practice guidelines to guide the management of subjects. Investigators must provide evidence of such qualifications through current CVs and other relevant documentation requested by the Sponsor, IRB, and regulatory agencies.

Investigators at the site are responsible for being familiar with the use of proposed investigational procedures, techniques and products, as described in current literature, product information, and other available sources. As part of their qualification to conduct the study, investigators are responsible for ensuring that investigational site resources are available and that the appropriate population of subjects can be identified/treated.

12.2 Clinical Investigation Plan Amendments

Approved CIP amendments will be provided to the investigators by the Sponsor prior to implementation. The Principal Investigator is responsible for notifying the IRB of the amendment (administrative changes) or obtaining IRB's approval of the amendment (changes in subject care or safety), according to the instructions provided by the Sponsor.

Acknowledgement/approval by the IRB of the CIP amendment must be documented in writing prior to implementation. Copies of this documentation must also be provided to the Sponsor.

12.3 Study Training

12.3.1 Site Training

Investigators and site clinical study personnel are required to attend Sponsor training sessions, which may be conducted at an investigator's meeting, a Site Initiation Visit (SIV) or other appropriate training sessions. Over-the-phone or self-training may take place as required. Training of investigators or site clinical study personnel will include, but is not limited to, the CIP requirements, investigational device usage, eCRF completion and study personnel responsibilities.

All investigators and site clinical study personnel that are trained must sign a training log (or an equivalent) upon completion of the training. Investigator/study personnel must not perform any study-related activities that are not considered standard of care at the site prior to signing the training log.

12.3.2 Training of Sponsor's Designees or Vendors

All Sponsor partners and/or designated vendors (e.g., Echocardiography Core Laboratory) responsible for any function in the conduct of the clinical study will be trained to the CIP and other study documents (as appropriate).

12.3.3 Training of Sponsor's Monitors

Sponsor and/or designated monitors will be trained to the CIP, eCRFs and investigational device usage (as appropriate). Documentation of this training will be according to written procedures.

12.4 Monitoring

The Sponsor and/or designee will monitor the study over its duration according to the monitoring plan and relevant standard operating procedures.

12.4.1 Designated Monitors

Study monitors are individuals who are designated to oversee the progress of a study. These individuals are appropriately trained and qualified to monitor the progress of a clinical study. The study Sponsor may designate additional monitors at any time during the study. To request information on the person(s) responsible for monitoring activities, contact the Sponsor at the following address:

Abbott Global Clinical Operations
[name]
[name]

12.4.2 Monitoring Visits

Scheduled visits to an investigational site may occur at the following times: prior to the start of the clinical study (pre-site qualification visit), at initiation of the study (at first implant or shortly thereafter), interim visits throughout the clinical study as required, and upon completion of the clinical study as outlined in the study monitoring plan.

12.5 Deviations from Clinical Investigation Plan

The investigator will not deviate from the CIP for any reason without prior written approval from Sponsor except in cases of medical emergencies, when the deviation is necessary to protect the rights, safety and well-being of the subject or eliminate an apparent immediate hazard to the subject. In that event, the Investigator will notify Sponsor immediately by phone or in writing. All deviations must be reported to the Sponsor. For subject-specific deviations from the CIP, a deviation eCRF will be completed. The occurrence of CIP deviations will be monitored by the Sponsor for evaluation of investigator compliance to the CIP and regulatory requirements and dealt with according to written procedures. Investigators will inform their IRB of deviations in accordance with their specific reporting policies and procedures.

In the event of repeated non-compliance, the Sponsor, or designee, will attempt to secure compliance by one or more of the following (and not limited to):

- Visiting the investigator and/or delegate
- Telephoning the investigator and/or delegate
- Corresponding with the investigator and/or delegate

Repeated non-compliance with the signed agreement, the CIP or any other conditions of the study may result in further escalation in accordance with the Sponsor's written procedures including securing compliance or, at its sole discretion; Sponsor may terminate the investigator's participation in the study.

12.5.1 Deviations with Expedited Reporting Requirements

For the following types of protocol deviations (per 21 CFR 812.150), an investigator is required to notify the Sponsor and the IRB within five (5) business days of the deviation.

- Emergency deviation from the CIP (a deviation to protect the life or physical well-being of a subject in an emergency).
- Failure to obtain informed consent.

Notification to the Sponsor and/or the IRB should be documented and maintained in the clinical trial file at the site and at Tendyne Holdings, Inc.

12.5.2 Non-Critical Deviations

Protocol deviations which do not have the urgency associated with expedited notification or prior Tendyne/IRB approval (as discussed in the above paragraphs) will be reported upon discovery, such as during completion of eCRFs or during a monitoring visit.

